5.3 LIFESTYLE CONSIDERATIONS

Participants will be expected to follow protocol requirements for contraception (see [Appendix 5](#)), but there are no other lifestyle restrictions during the study. There are no study-specific restrictions to meals and dietary requirements.

5.4 SCREEN FAILURES

Screen failures are defined as participants who consent to participate in the clinical study, but are not subsequently entered in the study.

The Investigator will maintain a screening log to record details of all participants screened and to confirm eligibility or record reasons for screening failure. In the event that a fresh biopsy is taken during the screening period and the participant is not enrolled into the study, the FFPE biopsy block can be returned to the site upon site request. Similarly, screening stool samples of participants who are not enrolled in the study will be destroyed on site.

Individuals who fail to meet the criteria for participation (screen failures) may be re-screened, with Sponsor approval. In the event re-screening is permitted, invasive assessments like biopsies do not have to be repeated if agreed by Medical Monitor. Re-screened participant should be assigned a different screening number as compared to that used for the initial screening.

Biopsy samples will only be entered in the electronic case report form (eCRF) and analyzed for enrolled participants.

Participants who are re-screened are required to sign a new Informed Consent Form (ICF).

5.5 RECRUITMENT PROCEDURES

Patients will be identified for potential recruitment by the investigator and referring physicians using pre-screening enrollment logs, clinical databases and Institutional Review Boards (IRB)/Independent Ethics Committees (IEC) approved newspaper/radio/social-media advertisements prior to consenting to take place on this study.

6. TREATMENTS

Study intervention is defined as any investigational product or marketed product intended to be administered to a study participant according to the study protocol. For the purpose of the study, RO7296682 is considered the Investigational Medicine Product (IMP). RO7296682 required for completion of this study will be provided as study medication by the Sponsor or its designee in compliance with local drug management regulations. Pre-medications are considered non-investigational medicinal products (NIMPs).

All study treatment administration will be at the study center under supervision of site staff.

6.1 TREATMENTS ADMINISTERED

The administered treatments are summarized in [Table 7](#). For more details, see the [RO7296682 IB](#) and pharmacy manual.

Study medication must be administered in a clinic or hospital equipped for systemic (IV) cancer treatment. Full emergency resuscitation facilities should be immediately available, and participants should be under close observation by the Investigator/site staff at all times. In case of infusion associated AEs, the signs and symptoms should be fully resolved before the patient is discharged.

Guidelines for dosage modification and treatment interruption or discontinuation are provided in [Section 6.6](#) and [Section 7.1](#) respectively for RO7296682, and in [Section 8.2](#).

For information and guidance on pre-medication, see [Section 6.1.2](#) and [Table 8](#).

[figure not shown]
Table 7 Summary of Treatments Administered

	Ro 729-6682/F01 (active)	Ro 729-6682/F02 (diluent)
Dose Formulation:	Solution for infusion	Solution for infusion
Unit Dose Strength(s)/Dosage Level(s):	20 mg/mL	0 mg/mL
Dose:	Ascending flat doses with starting dose of 0.3 mg	Not applicable
Route of Administration:	IV infusion*	IV infusion*

- * 0.2 µm in-line filter to be used for drug administration

6.1.1 RO7296682 and Infusion Rates

RO7296682 will be administered by IV infusion over 4 hours (240 min) at the first infusion. If the first infusion is well tolerated, as defined by an absence of Grade ≥ 2 IRRs, the second infusion may be given over 2 hours (120 min). If the 2-hour infusion is well tolerated, all subsequent infusions may be further reduced to 60 minutes. If the previous infusion was not well tolerated, RO7296682 should be infused at the previous infusion rate. In case this infusion is well tolerated again, subsequent infusion may be reduced as previously described. Please refer to [Section 6.1.2](#) and [Section 8.3.8](#) for premedication and IRR management guidelines, respectively. Ro 729-6682/F01 (active) solution for infusion should be used undiluted or diluted in the Sponsor's Diluent Ro 729-6682/F02 solution prior to administration. A 0.2 µm in-line filter must be used with the infusion set during administration.

6.2 PREPARATION/HANDLING/STORAGE/ACCOUNTABILITY

Study drug packaging will be overseen by the Roche clinical trial supplies department and bear a label with the identification required by local law, the protocol number, drug identification and dosage.

The packaging and labeling of the study medication will be in accordance with the Sponsor's standard and local regulations.

The study site should follow all instructions included with each shipment of IMP and diluent. The investigational site will acknowledge receipt of IMPs and confirm the shipment condition and content. Any damaged shipments will be replaced. The Investigator or designee must confirm that appropriate temperature conditions have been maintained during transit for all IMPs received and that any discrepancies have been reported and resolved before use of the IMPs. All IMPs must be stored in a secure, environmentally controlled, and monitored (manual or automated) area in accordance with the labeled storage conditions, with access limited to the Investigator and authorized staff.

Only participants enrolled in the study will receive IMPs, and only authorized staff will supply or administer IMPs.

The study site (i.e., Investigator or other authorized personnel) is responsible for maintaining records of IMP delivery to the site, IMP inventory at the site, IMP use by each participant, and disposition or return of unused IMP, thus enabling reconciliation of all IMP received, and for ensuring that participants are provided with doses specified by the protocol.

Upon arrival of the IMPs at the site, site personnel will complete the following:

- Check the IMPs for damage.
- Verify proper identity, quantity, integrity of seals and temperature conditions.
- Report any deviations or product complaints to the Monitor upon discovery.

The qualified individual responsible for dispensing the study treatment will prepare the correct dose according to the Pharmacy Manual.

The Investigator or delegate must confirm appropriate temperature conditions have been maintained during transit for all study treatment received and any discrepancies are reported and resolved before use of the study treatment.

Only participants enrolled in the study may receive study treatment and only authorized site staff may supply or administer study treatment. All study treatments must be stored in a secure, environmentally controlled, and monitored (manual or automated) area in

accordance with the labeled storage conditions with access limited to the Investigator and authorized site staff.

The Investigator is responsible for study treatment accountability, reconciliation, and record maintenance (i.e., receipt, reconciliation, and final disposition records).

IMPs will either be disposed of at the study site according to the study site's institutional standard operating procedure (SOP) or returned to the Sponsor with the appropriate documentation. The site's method of IMP destruction must be agreed upon by the Sponsor. Local or institutional regulations may require immediate destruction of used IMP for safety reasons. The site must obtain written authorization from the Sponsor before any IMP is destroyed, and IMP destruction must be documented on the appropriate form. Accurate records of all IMPs received at, dispensed from, returned to, and disposed of by the study site should be recorded on the drug accountability log.

Refer to the pharmacy manual and/or the Investigator's Brochure for information on IMP formulation, IMP handling, including preparation and storage, and accountability.

6.3 MEASURES TO MINIMIZE BIAS: RANDOMIZATION AND BLINDING

6.3.1 Method of Treatment Assignment

This is an open-label study with no randomization.

The Sponsor will be responsible for allocation of patient numbers using an interactive voice/web response system (IxRS) process. The log in information and directions for the IxRS will be provided to each site.

Participants who fulfill all of the inclusion criteria and none of the exclusion criteria are eligible to participate in the study and will be assigned to a treatment group/dose in consultation with the Sponsor.

6.3.2 Blinding

Not applicable. This is a non-randomized, open-label study.

6.4 TREATMENT COMPLIANCE

The qualified individual responsible for dispensing the study treatment will prepare the correct dose according to the cohort assignment. This individual will write the date dispensed and participant number on the study treatment vial label and on the Drug Accountability Record. This individual will also record the study treatment number received by each participant during the study.

6.5 CONCOMITANT THERAPY

6.5.1 Permitted Therapy

Any medication or vaccine (including over-the-counter [OTC] or prescription medicines, approved dietary and herbal supplements, nutritional supplements) used by a participant during screening until the follow-up visit must be recorded along with reason for use, dates of administration (including start and end dates) and dosage information (including dose and frequency). All concomitant medications should be reported to the Investigator and recorded on the Concomitant Medications eCRF. All medication administered to manage AEs should be recorded on the Adverse Event eCRF.

The Medical Monitor should be contacted if there are any questions regarding concomitant or prior therapy.

Radiotherapy

The use of limited field palliative radiotherapy should be discussed by the Investigator on a case-by-case basis with the Medical Monitor in order to exclude overall progressive disease. When applicable, this type of radiotherapy is allowed at any time during the study, except for:

- Days where RO7296682 is administered

Treatment with RO7296682 should be on hold for participants who require short courses of palliative radiation for pain control and may be resumed following completion of radiation.

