n)	The auto-antibody panel will be assessed at Screening, pre-dose Cycles 2 and 3, and every 6 cycles thereafter. In participants who develop signs and/or symptoms suggestive of auto-immune disease while on-treatment, the auto-antibody panel must be repeated. Participants with confirmed positive serology of at least one of the auto-antibody panel during the course of the study should be discussed between Sponsor and Investigators, and if judged clinically relevant, could be referred to a specialist to exclude an underlying auto-immune disease.

Table 1 Schedule of Activities Treatment Period, 21-day Cycles, Q3W (cont.)

o)	Tumor assessments to be performed according to RECIST 1.1. (Appendix 7). Tumor lesions will be assessed at screening, and every 8 weeks (± 7 days) after first dose (i.e. C1D1) – regardless of any treatment delays – for the first year, and then every 12 weeks (± 7 days) thereafter until disease progression. For participants who discontinue treatment for any other reason than disease progression: a) an end of treatment CT/MRI scan is only to be performed if it was done ≥ 28 days prior to this day, b) CT/MRI scan to be performed at the Safety Follow-Up visit.
p)	Chest X-ray will be performed at baseline, if the baseline tumor assessment does not image the chest/thorax and as clinically indicated during the study treatment period.
q)	End of Treatment (EoT)/ Early Discontinuation Visit: Participants who complete treatment or discontinue early, will be asked to return to the clinic within 28 (+/-7) days after the last dose. The visit at which a response assessment shows progressive disease may be used as the discontinuation visit.
r)	Safety Follow-Up: Participants who complete the study or discontinue from the study early, will be asked to return to the clinic 90 (± 7) days after the last dose treatment with RO7296682. A tumor assessment is to be performed for participants who discontinued the study for reasons other than disease progression.
s)	Survival Follow-Up: The sites will provide to the Sponsor an update on survival status and new anti-cancer treatment 90 (± 7) days after the Safety Follow-Up visit and then every 3 months (± 14 days) thereafter up until 24 months post initial treatment (or until study closure) for each participant enrolled in the study. Contact can be either in person or via a phone call to document.

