5.1 INCLUSION CRITERIA

General Inclusion Criteria

Participants are eligible to be included in the study only if all of the following criteria apply prior to dosing on C1D1.

1. Signed written informed consent and ability to comply with the study protocol according to International Council for Harmonisation of Technical Requirements for Pharmaceuticals for Human Use (ICH) and local regulations.

Type of Participants and Disease Characteristics

2. Age \geq 18 years
3. Diagnosis of advanced and/or metastatic solid tumors (**Part A:** TNBC, OvC, MEL, NSCLC, HNSCC, or EsC; **Part B:** MEL, HNSCC, or NSCLC) who have progressed on all standard therapies, are intolerant to SOC, and/or are non-amenable to SOC. Participants whose tumors have a known sensitizing mutation must have experienced disease progression (during or after treatment) or intolerance to treatment with a respective targeted therapy.
4. Measurable disease according to RECIST v1.1
 - Previously irradiated lesions must not be counted as target lesions unless there has been demonstrated progression in the lesion and no other target lesions are available.
 - Lesions that are intended to be biopsied must not be counted as target lesions.

Note: In case a patient has just one target lesion, no baseline and/or on-treatment biopsy is required as this would exclude the patient from study participation.

5. Life expectancy, in the opinion of the investigator, of \geq 12 weeks

6. Eastern Cooperative Oncology Group (ECOG) Performance Status of 0 or 1 (Section 8.2.11).
7. Able to provide the most recent archival tumor tissue samples (formalin-fixed-paraffin-embedded [FFPE] blocks preferred; if not available, slides accepted).
 - In the absence of sufficient archival tissue, a fresh biopsy from a safely accessible site, per Investigator determination and patient consent, will be requested, providing the patient has more than one measurable target lesion. Note: if fresh biopsy cannot be obtained, please contact the Medical Monitor.
8. Adequate cardiovascular function:
 - Left ventricular ejection fraction $\geq 50\%$, as determined by multiple-gated acquisition scan (MUGA) or transthoracic echocardiogram (TTE)
 - New York Heart Association (NYHA) Heart Failure Stage ≤ 2
 - Baseline-corrected QT (QTcF) interval ≤ 470 ms
 - Resting systolic blood pressure ≤ 150 mmHg and diastolic blood pressure ≤ 100 mmHg (average of ≥ 3 readings)
 - Resting heart rate (HR) between 45-100 bpm

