Specific Inclusion Criteria for Part A (only for Participants who reached the “Tissue Biomarker Dose”) and Part B Dose Expansion cohorts:

15. A freshly collected biopsy of a tumor lesion (primary and/or metastatic) from a safely accessible site, per Investigator determination and patient consent, will be requested, providing the patient has more than one measurable target lesion. The biopsied lesion must not be a target lesion (see inclusion criteria 4). The following rules apply:
 - Bone lesion biopsies, bronchoscopy/trans-bronchial biopsies, and cytology fine needle aspirates are not acceptable.
 - The tumor lesion must not be a metastatic lymph node sample; metastatic lymph node is acceptable ONLY when other accessible tumor sites are not available for biopsy.
 - Fresh biopsies must be obtained within 28 days before the first dose at C1D1.
 - If fresh tissue biopsies cannot be obtained, please contact the Medical Monitor.
16. Consent to provide a freshly collected skin punch biopsy. Note: if fresh skin punch biopsy cannot be obtained, please contact the Medical Monitor.

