 - at least 5 half-lives or 28 days (whichever is shorter) have elapsed since prior treatment with specific immunomodulators, TLR agonists, inhibitors of IDO/TDO, or agonists (e.g., OX40) and the proposed C1D1
21. Prior treatment with a CC chemokine receptor 4 (CCR4)-targeting (e.g. mogamulizumab) or a CD25-targeting agent (e.g. basiliximab) is prohibited.
22. Treatment with standard radiotherapy, any chemotherapeutic agent, targeted therapy, or treatment with any other investigational drug (defined as treatment for which there is currently no regulatory authority-approved indication) within 28 days or 5 half-lives of the drug (whichever is shorter), prior to the first RO7296882 administration on C1D1.
23. Immuno-modulating agents:
 - Last dose with immuno-modulating agents such as e.g. etanercept, infliximab, tacrolimus, cyclosporine, mycophenolic acid, alefacept, or efalizumab (or similar agents) within 28 days or 5 half-lives of the drug (whichever is shorter) prior to C1D1.
 - Regular immunosuppressive therapy (i.e., autoimmune disease, chronic rheumatologic disease), and/or previous recipient of allotransplantation even if not in need of immunosuppressive therapy.
24. Treatment with systemic immunosuppressive medications including, but not limited to, prednisone, cyclophosphamide, azathioprine, methotrexate, thalidomide, and anti-Tumor Necrosis Factor (TNF) agents within 2 weeks prior to C1D1. Participants who have received acute and/or low-dose systemic immunosuppressive medications (e.g. a one-time dose of dexamethasone for nausea or chronic use of ≤ 10 mg/day of prednisone or another dose-equivalent corticosteroid) may be enrolled in the study after discussion with and approval by the Medical Monitor. The use of inhaled corticosteroids and mineralocorticoids (e.g. fludrocortisone) is allowed.
25. Radiotherapy within the last 4 weeks before start of study drug treatment, with the exception of limited palliative radiotherapy (for which no wash out period is required).
26. Adverse events from any prior anti-cancer therapy that have not resolved to Grade ≤ 1 except for alopecia, vitiligo, or endocrinopathy managed with replacement therapy, and Grade ≤ 2 peripheral neuropathy. Note: Other Grade 2 AEs that are deemed clinically insignificant by treating physician and in consultation with Medical Monitor are permitted.

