Objective response rate (ORR) is determined as the rate of participants with an overall response of CR or PR. Disease control rate is determined as the rate of participants with an overall response of either CR, PR, or SD rate. ORR and DCR will be derived for RECIST Version 1.1 and will be based on Investigators' assessment. Objective response (OR) is defined as a CR or PR as determined by the Investigator. For this protocol, confirmation of response is required at least 4 weeks after a first response occurred. To classify a response as SD, measurements will have to be classified as stable (according to RECIST Version 1.1) at least once after study entry at a minimum of 6 weeks after study entry. Participants with missing or no response assessments will be classified as not evaluable unless there is documented clinical deterioration, in which case participant will be classified as non-responders.

DoR will be calculated for participants who have a best overall response of CR or PR and will be defined as the time from first occurrence of a documented OR until the time of documented disease progression or death (death within 30 days from last study

treatment) from any cause, whichever occurs first. Censoring methods will be the same as the one applied for progression-free survival (on-treatment PFS).

PFS on treatment will be defined as the time from study treatment initiation (C1D1) to the first occurrence of documented disease progression (based on RECIST Version 1.1 Investigator's assessment) or death from any cause, whichever occurs first. For participants who do not have documented progressive disease or death (within 30 days from last study treatment) during the study, PFS will be censored at the day of the last tumor assessment. Participants without any post baseline assessments or with all post-baseline assessments having unknown result/response but known to be alive at the clinical cut off for the analysis will be censored at the date of study treatment initiation plus one day.

Sensitivity analyses of response endpoints (ORR, DRC, DoR, and PFS) may include the evaluation of response according to iRECIST. As a sensitivity analysis, the analysis described in [Table 13](#) may be applied to a more generic definition of PFS that also includes deaths occurring more than 30 days after last study treatment. Secondary analyses of response endpoints may (if implemented) include the evaluation of response.

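### A target lesion given palliative radiotherapy on study stays in the sum of diameters, so its shrinkage can be scored as a response to RO7296682

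*Combined protocol and SAP*

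**What the plan says.** **Radiotherapy.** Before entry, exclusion criterion 25 bars recent radiotherapy "with the exception of limited palliative radiotherapy (for which no wash out period is required". On study, section 6.5.1 has the investigator discuss limited-field palliative radiotherapy "on a case-by-case basis with the Medical Monitor in order to exclude overall progressive disease". Subject to that, "this type of radiotherapy is allowed at any time during the study, except for" days on which RO7296682 is given. The section adds: "Treatment with RO7296682 should be on hold for participants who require short courses of palliative radiation for pain control".

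**Target lesions.** Inclusion criterion 4 states: "Previously irradiated lesions must not be counted as target lesions unless there has been demonstrated progression in the lesion", and then only if no other target lesion is available. Appendix 7 (1.1.3) treats irradiated lesions as usually not measurable and leaves the conditions to the protocol. Both rules concern selection at baseline. After baseline, Appendix 7 sums the diameters of all target lesions (2.2), requires each to be measured at every evaluation (2.3.2), and calls a fall of at least 30% from the baseline sum a PR (2.3.1). Section 9.4.2 requires confirmation at least 4 weeks later.

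**Biopsies.** Criterion 15 states: "The biopsied lesion must not be a target lesion (see inclusion criteria 4". Criterion 15 and section 8.8.1 list unacceptable sites and sampling methods; irradiated lesions are not among them.

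**Late scans.** Participants who stop treatment without progression are scanned at Safety Follow-Up, and at End of Treatment if the last scan was at least 28 days earlier (Table 1, footnote o). Footnote r repeats the former: "A tumor assessment is to be performed for participants who discontinued the study for reasons other than disease progression". For those without progression or death within the 30-day limit, "PFS will be censored at the day of the last tumor assessment"; DoR follows the same censoring. Section 6.5.2 prohibits other anti-cancer therapy during the study.

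**The concern.** Criterion 4 recognises that a change in an irradiated lesion cannot be read as drug effect, but the plan does not carry that principle past baseline. The study has no control arm, so attribution of a response to RO7296682 rests entirely on the scoring rules. Followed as written, they turn shrinkage from radiotherapy into an objective response.

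The endpoints affected are secondary: ORR, DCR, DoR and PFS, and the Treg and Treg/Teff changes in tumor. They still feed decisions. Efficacy is summarised by dose cohort (9.4.2), and an objective response is one of the triggers for starting on-treatment biopsies in the next cohort (1.1). The PD endpoint in 9.4.6 is judged against a 50% threshold, and the MTD and/or RP2D draws on the PK/PD profile (4.1).

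**Working it through.** The plan has no figure of its own to reproduce: there is no hypothesis test, and no frequency of radiotherapy or later therapy is given. The check is a reading of the rules, with illustrative arithmetic.

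**1. Can an irradiated target lesion produce a PR?** Let f be its share of the baseline sum and s its proportional shrinkage, with other target lesions unchanged (assumption). The sum falls by f × s, and PR needs f × s ≥ 0.30, so s ≥ 0.30 / f.

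| Share f | Shrinkage needed |
|---|---|
| 0.40 | 0.30/0.40 = 75% |
| 0.50 | 0.30/0.50 = 60% |
| 0.60 | 0.30/0.60 = 50% |
| 0.80 | 0.30/0.80 = 37.5% |

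Confirmation does not remove the problem. It protects against measurement error (Appendix 7, 2.6.1), and real shrinkage that persists to the next scan is confirmed.

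**2. Can it delay a PD based on the sum?** Take baseline as the smallest sum, both changes seen on the same scan, and leave aside the 5 mm minimum. The other lesions must then grow by (0.20 + f × s)/(1 − f). With f = 0.30 and s = 0.50 this is (0.20 + 0.15)/0.70 = 50.0%, against 0.20/0.70 = 28.6% if the irradiated lesion is static. New lesions and unequivocal non-target progression still count as PD.

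**3. What is one response worth?**
- Part B at its maximum: 1/50 = 2 points. Exact (Clopper-Pearson) 90% intervals are 0 to 5.8% for 0/50 and 0.1 to 9.1% for 1/50; the plan does not name the interval method.
- A Part A cohort at the minimum of 3: 1/3 = 33 points.

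**4. Biopsy pairs.** Criterion 4 sends most lesions irradiated before baseline to the non-target group, and criterion 15 draws the biopsy from outside the targets. One pair of the planned 20 is 1/20 = 5 points, the step between 9/20 (45%) and 10/20 (50%) at the 9.4.6 threshold.

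**5. Scans after new therapy.** End of Treatment falls 21 to 35 days after the last dose (28 ± 7) and Safety Follow-Up 83 to 97 days (90 ± 7).
- Gap: 83 − 35 = 48 days at shortest, 97 − 21 = 76 at longest, both above the 28 days needed for confirmation.
- The Safety Follow-Up scan lies 83 − 30 = 53 to 97 − 30 = 67 days beyond the 30-day limit applied to deaths in on-treatment PFS.
- Section 9.4.2 has no cut-off or censoring at new therapy for ORR, DCR, DoR or PFS.

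**The case against.** Several stronger readings are tempting, and the documents do not support them.

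- A reader might infer that the missing washout puts freshly irradiated lesions into the response sums. Criterion 4 largely prevents this; the missing washout bears mainly on the biopsied lesion.
- A reader might infer that radiotherapy on study is unrestricted. It is barred on infusion days, discussed case by case to exclude progression, and accompanied by a drug hold for short pain courses. These safeguards govern conduct, however, and do not change how the lesion is scored.
- A reader might infer that the plan counts scans made after new therapy. It does not say so. Section 6.5.2 prohibits such therapy during the study, and the 90-day visit is labelled End of Study, so on a plain reading that scan falls inside the prohibition. What remains is breaches, or therapy started after RO7296682 stops and before that scan. For new therapy alone to give a confirmed response, it would have to act by the End of Treatment scan, because the Table 1 footnotes schedule no scan after Safety Follow-Up to confirm a response first seen there.
- A reader might infer that every effect flatters the drug. For PFS and DoR this is not shown: late scans also capture progressions, and censoring at new therapy can raise Kaplan-Meier estimates. The direction in which radiotherapy moves tumor Tregs is not shown either.

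Other limits also stand. Parts of 9.2 (tumor biopsy samples) and 4.2.2 are redacted, so a pair-evaluability rule may exist out of sight. Bone biopsies are barred and blastic bone lesions are non-measurable, which lowers the risk to the extent that palliative fields are bone. The endpoints are descriptive, and the primary AE and DLT endpoints are untouched. None of this supplies a rule for a target lesion irradiated on study.

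**Conclusion.** The point holds for target lesions irradiated after baseline: the stated rules, applied literally, can score the effect of radiotherapy as a confirmed PR. This is a defect in scoring, not only missing detail, and is worth correcting although the endpoints are secondary.

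The biopsy gap is real in the visible text, subject to the redactions; an affected pair is uninterpretable, not necessarily favourable. The new-therapy gap is narrow because of the prohibition in 6.5.2.

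The size of the bias cannot be computed. One misattributed response is 1/n of the cohort: 2 points at n = 50, 33 points at n = 3. The shrinkage figures assume that the other target lesions do not change, and confirmation assumes that the shrinkage persists.

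**What to change.** **Response (9.4.2 and Appendix 7).** From the date of on-study irradiation, a target lesion is still measured and can show PD. A time point that reaches the CR or PR threshold only because of that lesion's shrinkage is not counted as CR or PR. One workable test is to recompute the sum with the lesion held at its last measurement before irradiation. The rule should name the category given instead, for example SD subject to the existing 6-week minimum, because unable to assess (Appendix 7, 2.4.2) would give a different DCR. Record the irradiated site and date in the eCRF.

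**New therapy (9.4.2).** Do not count toward ORR or DCR any assessment made after new anti-cancer therapy starts; capture its start date. Keep the planned PFS and DoR, and add a sensitivity analysis censored at the last assessment before that date.

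**Biopsy pairs (9.4.6 and 8.8.1).** Flag pairs whose lesion was irradiated within 4 weeks before the baseline biopsy or between the two biopsies, and exclude them from the evaluable pairs. The 4 weeks is borrowed from criterion 25, where it runs to the start of study drug, so it should be stated as a convention.

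**Cost.** Wording and a few data fields; concomitant treatment is already monitored, and new anti-cancer therapy is already reported at survival follow-up. A few responses or pairs would no longer count, and ORR may be slightly lower. Delay of a PD based on the sum (step 2 of the working) is not corrected, but a listing of participants irradiated on study would make it visible. No change to access to radiotherapy is proposed.
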